## **STUDY OVERVIEW**

- Eligible patients with 1-3 painful osseous metastases will receive a consultation and subsequently undergo CT simulation, radiation treatment planning, and their first radiation treatment on day 1.
- Patients will receive a total of 2-5 fractions of high dose palliative radiation therapy via helical TomoTherapy consisting of 5-10 Gray (Gy) per fraction with a minimum biologic effective dose (BED) of 25 Gy.
- Standard patient-specific treatment planning quality assurance will be performed on a cylindrical phantom with ion chamber and film measurement.
- Software provided by TomoTherapy Inc.® will be used to measure the radiation exiting the patient and recalculate the dose the patient received. This calculated dose will then be compared to phantom measurements and treatment planning calculations to validate the ability of this novel radiation dose verification software to verify the accurate delivery of radiation. This will not replace standard quality assurance measurements.
- At the Emily Couric Cancer Center, an in-house developed infrared motion tracking system will monitor patients' positions for any deviation from the treatment position. This is not standard of care but may augment standard safety measures with full implementation in the future and does not subject the patient to any risks or discomfort. Infrared motion tracking is will be optional and not required for patients treated at CRH.
- Contouring (the demarcation of the tumor and critical structures) will be performed in the standard manner for treatment planning.
- Contouring will also be performed in an expedited, experimental manner on diagnostic image sets which will then be compared to the standard contours. Experimental contouring will not replace standard contouring, nor affect treatment planning.
- Patients will complete questionnaires to capture pain scores of the treated lesion(s), analgesic use, patient functional status, patient quality of life, and patient satisfaction at 1 week, 4 weeks, 8 weeks, 12 weeks, 6 months, and 12 months following treatment. These scores will be compared to questionnaires completed pretreatment.
- Radiation-induced toxicities will be captured during treatment physical examinations and at follow-up physical examinations at 4 weeks, 12 weeks, 6 months, and 12 months.

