**Primary Specific Aim/ Hypothesis:** We will quantify the time for pain relief, amount of pain relief, opioid use reduction, functional scores, quality of life, and satisfaction of patients treated with STAT RT for osseous metastases. We hypothesize that these patients will have rapid and significant pain relief, improved quality of life, and high patient satisfaction.

**Secondary Specific Aim/ Hypothesis:** We will optimize the integration of commercially available and in-development software to develop the Scan-Plan-Treat STAT RT workflow. Specifically, we will A) optimize rigid and deformable co-registration of pre-contoured diagnostic image sets to MVCT simulation scans and compare the accuracy to the same pre-contoured diagnostic image sets co-registered to kilovoltage CT (kVCT) simulation images and then

kVCT simulation to MVCT scan co-registration, B) optimize CT-detector-based exit dose measurement algorithms for quality assurance and compare to standard of care phantom-based quality assurance, C) explore the options of including an in-house real time infrared tracking system for intrafractional patient position monitoring to ensure accurate patient treatment. We hypothesize that these new components will provide effective and efficient methods for treatment planning, quality assurance, and patient position monitoring that can be used in a future 30 minute Scan-Plan-Treat STAT RT workflow.

**Study design:** We will recruit 30 cancer patients with 1-3 painful osseous metastatic lesions (target sites) who are candidates for palliative radiation therapy. Patients will receive 2-5 fractions of 5-10 Gy (minimum BED of 25 Gy) of conformal radiation therapy delivered to the target sites via the Helical TomoTherapy system using the STAT RT workflow. Data will be collected to evaluate the effectiveness of our novel image co-registration techniques and CT-detector-based exit dose calculations. These novel techniques for image co-registration, radiation dose calculations, and possible patient position monitoring will not alter or replace standard of care techniques. Using validated surveys we will record patient pain, analgesic use, function, quality of life, and patient satisfaction prior to treatment and at 1 week, 4 weeks, 8 weeks, 12 weeks, 6 months, and 12 months after therapy. Radiation-induced treatment related toxicities will be captured during treatment and at the above time points.

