## **2.0 STUDY OBJECTIVES**

### **2.1 Primary Objectives**

Our primary objectives are to quantify outcomes of patients with osseous metastases treated via the STAT RT workflow. Specifically, we are plan to:

- 2.1.1** Estimate the response to palliative radiation as defined by International Bone Metastases Consensus Group using the BPI and OMED to categorize into Complete Response, Partial Response, Pain Progression, and Stable Pain after receiving treatment via the STAT RT workflow.
- 2.1.2** Estimate the change in the patient's quality of life and function as scored by FACT-BP and KPS after receiving treatment via the STAT RT workflow.
- 2.1.3** Estimate patient satisfaction with the STAT RT workflow using a modified FACIT-TS-BTCSQ survey.
- 2.1.4** Report the treatment-related toxicity using CTCAE Version 4 and RTOG Late Radiation Morbidity Scoring Criteria after receiving treatment via the STAT RT workflow.

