## **6.0 EVALUATION CRITERIA**

### **6.1 Response to Palliative Radiotherapy**

#### **6.1.1 Response Criteria According to the International Bone Metastases Consensus Group**

Complete Response (CR): Pain reduction to zero AND OMED\* stable or reduced

Partial Response (PR): Pain reduction by two scores or more AND OMED\* stable or reduced.  
OR  
Stable pain AND OMED\* reduction by 25% or more

Pain Progression (PP): Pain increase by two scores or more AND OMED\* stable or increased.  
OR  
No change in pain AND OMED\* increased by 25% or more (or start of morphine use after the baseline or epidural pain treatment at follow-up)

Stable Pain (SP): Stable pain AND stable OMED\*

OMED = Oral Morphine Equivalent Dose

\* The total OMED intake over the most recent 72 hours will be calculated at each evaluation.

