**1) Primary Aim: Evaluation of Outcomes of Patients with Osseous Metastases Treated with STAT RT**

We will recruit 30 cancer patients with 1-3 painful osseous metastatic lesions (target sites) requiring opioid medication who are candidates for palliative radiation therapy. Patients will receive 2-5 fractions of 5-10 Gy (minimum BED of 25 Gy) of conformal radiation therapy delivered to the target sites via the Helical TomoTherapy system using the STAT RT workflow. Patient pain, analgesic use, function, quality of life, and satisfaction will be recorded prior to treatment, at 1 week, 4 weeks, 8 weeks, 12 weeks, 6 months, and 12 months after therapy using the following measures:

- a) The Brief Pain Inventory (BPI)
- b) Patients will keep an analgesic use logbook and have their doses converted into Oral Morphine Equivalent Doses (OMED).
- c) Treatment response will be measured by the guidelines set forth by the International Bone Metastases Consensus Group as described in Section 6.1.1.
- d) The FACT-BP and FACT-G questionnaires
- e) Karnofsky Performance Scale (KPS)
- f) Patient Satisfaction will be measured by a modified FACIT-TS-BTCSQ survey.

Radiation-induced treatment related toxicities will be captured during treatment and at the above time points and graded using the CTCAE Version 4.0 and the RTOG Late Radiation Morbidity Score Criteria.

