### **7.3 Data Analyses Plans**

Treatment response as defined by International Bone Metastases Consensus Group will be determined for each patient. As described in Section 6.1.1, pain intensity as defined by the BPI and opiate use as quantified by the OMED will be used to categorize patients as having: Complete Response, Partial Response, Pain Progression, Stable Pain. At each evaluation, the patient's BPI and OMED at that visit will be compared to the pre-treatment levels. The "Worst Pain" score from the patient's BPI will be used to evaluate for treatment response. Patient response does not require a statistical analysis. The percentage of patients in each response category at each evaluation will be reported.

Patient pain will be recorded using the BPI before treatment and at designated evaluations after treatment. Pain scores before and after treatment will be compared using a Wilcoxon signed ranks test to determine if there is a statistically significant difference. Example: Pre-treatment vs. 1 week, Pre-treatment vs. 4 weeks, etc.

Analgesic use will be recorded by requiring each patient to keep a logbook of their analgesic intake. Their opiate intake for the last 72 hours will be converted to OMED at each evaluation and used in the categorization of treatment response. The difference between their OMED before and after treatment will be compared using paired two-sample t-tests.

Patients' functional status will be determined using the Karnofsky Performance Scale at each evaluation. The difference between the KPS before and after treatment will be compared using a Wilcoxon signed ranks test.

Patients' quality of life will be measured using FACT-BP and FACT-G scores at each evaluation. The difference between the FACT scores before and after treatment will be compared using a Wilcoxon signed ranks test.

Patient satisfaction will be measured using a modified version of FACT - TS – BTCSQ. No statistical analysis will be required for reporting the results. The average scores from the satisfaction survey will be reported.

To evaluate the CT detector dose calculations, the delivered radiation dose obtained using the phantom quality assurance will be compared to the exit radiation dose quality assurance calculation. The calculated dose and delivered dose for each patient will be compared using a paired two-sample t-test, and the % difference in dose will be reported.

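### Response is a primary estimation objective, but 7.3 reports bare percentages with no interval or stated denominator, and the opioid logbook stops at week 12 although every response category needs opioid dose

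*Combined protocol and SAP*

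**What the plan says.** Section 2.1 lists four primary objectives without ranking them. The first is to "Estimate the response to palliative radiation as defined by International Bone Metastases Consensus Group", using the BPI and OMED.

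Section 7.3 compares each patient's BPI and OMED at a visit with the pre-treatment values and takes Worst Pain as the BPI item for response. It then says "Patient response does not require a statistical analysis" and continues: "The percentage of patients in each response category at each evaluation will be reported". No interval, denominator or rule for unassessed patients follows. The only evaluability rule, in 4.3 and 6.2, concerns toxicity.

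Section 5.4 expects a fair share of participants to choose hospice care before follow-up is complete. Section 7.2 relies on accruing 30 rather than 21 to absorb dropouts.

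On opioid dose, 6.1.1 says "The total OMED intake over the most recent 72 hours will be calculated at each evaluation", and 7.3 says "Their opiate intake for the last 72 hours will be converted to OMED at each evaluation", with the logbook as the source. The Study Overview lists "analgesic use, patient functional status, patient quality of life, and patient satisfaction at 1 week, 4 weeks, 8 weeks, 12 weeks, 6 months"; its last visit is at 12 months. The study design paragraph of 1.1 and the Primary Aim text of 7.1 ("Patient pain, analgesic use, function, quality of life, and satisfaction will be recorded prior to treatment", then at the same six visits) agree. The Time and Events table in 5.1 marks the logbook before and during treatment and at weeks 1, 4, 8 and 12 only. BPI is marked through month 12.

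**The concern.** An estimate from 30 patients has limited value without its precision, and a percentage has no fixed meaning until its denominator is known. Patients assessed at the visit is the natural reading, because 7.3 works from that visit's BPI and OMED, but it is not written. An analyst could equally divide by all treated patients. The two readings separate as patients are lost, and the protocol itself expects losses.

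The schedule problem is different in kind. Complete response, partial response, pain progression and stable pain all carry an OMED condition in 6.1.1. Without a scheduled OMED at 6 and 12 months, none of the four can be assigned there as defined, yet 7.3 promises the percentages at each evaluation. BPI item 7 asks which medications are taken, not the dose over 72 hours.

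**Working it through.** **Sample size first.** Inputs from 7.2: mean change 2, SD 3, two-sided alpha 0.05, power 80%, Wilcoxon signed-rank test, stated n = 21.

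- Standardised effect: d = 2/3 = 0.667.
- Noncentral-t power with effective size n × 3/π, the efficiency of the Wilcoxon test for normal differences. At n = 21 the effective size is 21 × 0.955 = 20.05 and the noncentrality is 0.667 × √20.05 = 2.99.
- Power is 0.787 at n = 20, 0.808 at n = 21 and 0.931 at n = 30. Simulating the signed-rank test at n = 21 gives 0.803.

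The stated 21 reproduces. For the anticipated 3-unit change, power at 21 pairs is 0.989. The plan leaves room for 30 − 21 = 9 unassessed patients at whichever visit is tested.

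**Precision and denominator of response.** The exact (Clopper-Pearson) 95% limits for x responders among n are:

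- lower = 2.5% quantile of Beta(x, n − x + 1)
- upper = 97.5% quantile of Beta(x + 1, n − x)

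Assumptions: about 80% response among those assessed, and 0, 3, 6 or 9 of 30 unassessed. Neither is a forecast, because the documents give no attrition rate.

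| Unassessed | Over those assessed | Over all 30 treated | Difference |
|---|---|---|---|
| 0 | 24/30 = 80.0% (61.4-92.3) | 24/30 = 80.0% (61.4-92.3) | 0 |
| 3 | 22/27 = 81.5% (61.9-93.7) | 22/30 = 73.3% (54.1-87.7) | about 8 points |
| 6 | 19/24 = 79.2% (57.8-92.9) | 19/30 = 63.3% (43.9-80.1) | about 16 points |
| 9 | 17/21 = 81.0% (58.1-94.6) | 17/30 = 56.7% (37.4-74.5) | about 24 points |

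The same 17 responders can therefore be reported as 81% or 57%.

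**OMED at late visits.** Three texts set side by side:

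- 5.1: logbook at four of the six follow-up visits (weeks 1, 4, 8, 12); BPI at all six.
- Study Overview, 1.1 and 7.1: analgesic use at all six, naming 6 and 12 months.
- 6.1.1 and 7.3: OMED at each evaluation, with no months listed. Read alone, these could mean each scheduled logbook evaluation.

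The explicit conflict is thus between 5.1 and the Study Overview, 1.1 and 7.1. The consequence for response comes from 6.1.1, where every category needs OMED, combined with 7.3, which reports response at each evaluation.

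**The case against.** The best defence is that this is a small, non-randomised pilot that describes its results. Every visit is reported, nothing is hidden, and a reader given the counts could compute an interval. That is fair as to intent. But where the aim is description, the interval and denominator are the analysis, and adding them requires no new test, patient or visit. It is also fair that a clinician might obtain opioid doses from the history taken at 6 and 12 months; no text says so, and 7.3 names the logbook as the source.

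Several stronger readings are tempting, and the documents do not support them.

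- *Thirty patients cannot separate 80% from 60%.* Sections 1.2.2 and 1.3.1 contrast about 60% pain improvement with conventional treatment and over 80% with SBRT. A reader might set that 20-point gap against the full width of the interval. The relevant distance is from the estimate to its lower limit: 80.0 − 61.4 = 18.6 points, so 24/30 excludes 60%, as does 22/27. The other rows of the table do not. Section 7.3 plans no test against either figure, and neither is stated to be consensus CR+PR.
- *The 80% power belongs to no comparison.* Under the assumptions of 7.2 it applies to any single visit-versus-baseline test with at least 21 pairs. Section 7.3 does name visits, as examples.
- *One visit must be made primary and the other p-values treated as descriptive.* The stated aim begins "We will quantify the time for pain relief, amount of pain relief, opioid use reduction". Visit-by-visit comparisons serve that aim, so a single primary visit is a preference here.
- *Nine of 30 will be lost early.* Section 5.4 speaks of losses before the end of a 12-month follow-up, and eligibility requires life expectancy beyond 12 weeks. The documents do not show losses of that size by week 12.

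**Conclusion.** The point holds in two parts. First, a primary estimation objective is reported without uncertainty and over an unwritten denominator. At full assessment the omitted interval is 61-92% around an observed 80%. Under assumed losses of 3, 6 or 9 of 30, the denominator alone shifts the rate by about 8, 16 or 24 points, with the upper end more plausible at 6 and 12 months than before. These shifts rest on assumed attrition and an assumed 80% response among those assessed.

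Second, the logbook schedule conflicts with the stated collection of analgesic use at 6 and 12 months, and consensus response cannot be classified at those visits from the scheduled data. This part needs no assumption about attrition.

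Neither part touches the sample size or invalidates the trial. The unnamed BPI item for the Wilcoxon test is missing detail only: Worst Pain is specified for response but not for that test.

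**What to change.** In 7.3, replace "Patient response does not require a statistical analysis" with: *CR+PR at each evaluation will be reported with an exact 95% CI, over all treated patients (unassessed not counted as responders) and over those assessed, with numbers dead, withdrawn or missing shown.*

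Reconcile the logbook row of the Time and Events table with 7.1 and 7.3. Either schedule the logbook at 6 and 12 months, or state that OMED-based response is not reported at those visits.

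As a clarification only, name Worst Pain as the BPI item for the Wilcoxon test.

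The cost is a few sentences in 7.3 and one table row, with no change to sample size or visits. Keeping OMED at 6 and 12 months adds two logbook entries and some patient burden; dropping it gives up consensus response there. The all-treated rate may be lower and may understate palliation where death is from the underlying cancer, which is why both denominators should be shown.

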## **5.0 EVALUATIONS AND ASSESSMENTS**

### **5.1 Time and Events Table**

|  | Pre-treatment | During treatment | Week 1 | Week 4 | Week 8 | Week 12 | 6-Month | 12-Month |
|--|----------------------|-------------------------|---------------|---------------|---------------|----------------|----------------|-----------------|
| Informed Consent                                   | X                    |                         |               |               |               |                |                |                 |
| History and PE                                     | X                    |                         |               | X             |               | X              | X              | X               |
| Karnofsky Performance Status                       | X                    |                         | X             | X             | X             | X              | X              | X               |
| Toxicity Evaluations                               |                      | X                       | X             | X             | X             | X              | X              | X               |
| Opiod Logbook Evaluation                           | X                    | X                       | X             | X             | X             | X              |                |                 |
| Brief Pain Inventory                               | X                    |                         | X             | X             | X             | X              | X              | X               |
| FACT-BP and FACT-G surveys                         | X                    |                         | X             | X             | X             | X              | X              | X               |
| Satisfaction and Convenience Survey                | X                    |                         | X             | X             | X             | X              | X              | X               |
| Quality Assurance                                  | X                    |                         |               |               |               |                |                |                 |
| Diagnostic Imaging (CT/MRI/PET CT)                 | X                    |                         |               |               |               |                |                |                 |

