### **5.3 Final Study Visit**

The final study visit will occur at the 12 month visit. See the Time and Events Table for assessments that will be performed. Patients removed from study for treatment-related adverse events will be followed until resolution or stabilization of the adverse event

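### The visit schedule omits the opioid logbook at 6 and 12 months, so the response categories and opioid-dose comparisons promised at every evaluation would stop at week 12

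*Combined protocol and SAP*

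**What the plan says.** The text places opioid dose at every follow-up.

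- Section 7.1 (Primary Aim) lists patient pain, analgesic use, function, quality of life and satisfaction, and sets the times: "satisfaction will be recorded prior to treatment, at 1 week, 4 weeks, 8 weeks, 12 weeks, 6 months, and 12 months after therapy". It names the logbook, converted to OMED, as the measure of analgesic use.
- Section 6.1.1 says of the response criteria: "The total OMED intake over the most recent 72 hours will be calculated at each evaluation".
- Section 7.3 repeats that the 72-hour opioid intake is converted to OMED at each evaluation and used to assign the response category. It then says: "The percentage of patients in each response category at each evaluation will be reported". It also plans paired t-tests of OMED before and after treatment.
- The Study Overview says questionnaires will capture pain scores and "analgesic use, patient functional status, patient quality of life, and patient satisfaction at 1 week, 4 weeks, 8 weeks, 12 weeks, 6 months", and then 12 months. The study design paragraph of Section 1.1 gives the same list: "analgesic use, function, quality of life, and patient satisfaction prior to treatment and at 1 week, 4 weeks, 8 weeks, 12 weeks, 6 months", and then 12 months.

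The schedule differs. In Section 5.1 the row "Opiod Logbook Evaluation" is ticked at pre-treatment, during treatment and weeks 1, 4, 8 and 12, and is blank under the 6-month and 12-month columns. The rows for the BPI, Karnofsky status, the FACT surveys and the satisfaction survey are ticked in both of those columns. For the 12-month visit, Section 5.3 says: "See the Time and Events Table for assessments that will be performed".

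**The concern.** Objective 2.1.1, the first primary objective, is the four-category consensus response built from BPI and OMED. Site staff normally work from the visit table, and here the protocol sends them to it for the last visit. If they follow it, they collect a pain score at 6 and 12 months but no opioid dose.

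A pain score alone cannot distinguish lasting relief from relief bought with more opioid, which is the distinction the consensus criteria are meant to make. The late visits also matter for the trial's rationale. Section 1.3.1 cites 3 to 6 months of palliation with conventional radiotherapy and a median of 13.6 months in one stereotactic series. Week 12 (84 days) falls just short of the lower end of that span.

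A small, separate gap sits in Section 6.1.2. Duration of complete response ends only when a partial response is documented. A patient who moves from complete response straight to stable pain or pain progression therefore has no end date.

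**Working it through.** **The plan's own figure.** The only calculated figure in the plan is n = 21 in Section 7.2 (mean BPI change 2, SD 3, two-sided alpha 0.05, 80% power, Wilcoxon signed-rank). With effect size 2/3, a noncentral t calculation and the sample size scaled by the Wilcoxon relative efficiency 3/π, the smallest n is 21, with power 0.808. The figure reproduces. It rests on BPI alone, so the point made here does not touch it.

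**Schedule against text.** Follow-up weeks come from the schema in Section 4.1 (6 months = week 26, 12 months = week 52).

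| Follow-up week | 1 | 4 | 8 | 12 | 26 | 52 |
|---|---|---|---|---|---|---|
| BPI, Section 5.1 | yes | yes | yes | yes | yes | yes |
| Opioid logbook, Section 5.1 | yes | yes | yes | yes | no | no |
| Analgesic use, Section 7.1 | yes | yes | yes | yes | yes | yes |

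The logbook row has all eight cells (two before follow-up, six after), and neighbouring rows carry ticks in the last two. The blanks are therefore in the table itself and do not come from the way the file was read.

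**Does the response need OMED?** Section 6.1.1 gives six routes to a category:

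- complete response (1): pain at zero, with OMED stable or reduced;
- partial response (2): pain down by at least 2 with OMED stable or reduced, or stable pain with OMED down by at least 25%;
- pain progression (2): pain up by at least 2 with OMED stable or increased, or unchanged pain with OMED up by at least 25%;
- stable pain (1): pain and OMED both stable.

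All six refer to OMED. The second progression route also has an alternative that needs no dose (new morphine use or epidural treatment). Pain alone can exclude categories; a score above zero, for example, is not a complete response. It cannot separate partial response, stable pain and progression when pain is unchanged.

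**Other sources of dose.**

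- BPI item 7 (Appendix H) asks which treatments or medications are taken, not the amount over 72 hours.
- The history and physical examination at 6 and 12 months is not described as a source of opioid dose.
- Section 5.4 asks for the logbook only on withdrawal.

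**Size, if the table is followed.**

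- Follow-ups with full response classification: 4/6 = 67%. The same count holds for OMED comparisons, taking one comparison per visit.
- Patient-evaluations, all 30 patients attending throughout: 30 × 6 = 180 planned; 30 × 2 = 60 without OMED; 60/180 = 33%.
- With losses, on an assumption that is not in the documents (50% assessed at 6 months, 25% at 12 months, none lost before): 30 × 4 + 15 + 7.5 = 142.5 evaluations; 22.5 without OMED; 22.5/142.5 = 16%.
- Longest observable OMED-based response: 12 − 1 = 11 weeks under the table; 52 − 1 = 51 weeks under the text; 11/51 = 22%.

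**The case against.** The strongest reply is that the blanks are a clerical slip. Section 7.3 requires every patient to keep a logbook and gives no end date. Section 5.4 asks for it at withdrawal whenever that happens, and only the 12-month visit is sent explicitly to the table. If sites keep collecting the logbook, nothing is lost. That is possible, and it is why the harm is stated as conditional. It does not tell a site which instruction to follow.

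Several narrower points stand in part:

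- The Study Overview and Section 1.1 speak of questionnaires and surveys, which BPI item 7 might loosely satisfy. The contradiction rests on Sections 6.1.1, 7.1 and 7.3.
- The figure of 60 is a maximum. Patients on no opioid may be identifiable from item 7 and could be classified with an OMED of zero. Section 7.1 describes the population as having "painful osseous metastatic lesions (target sites) requiring opioid medication", but the eligibility criteria in Section 3 contain no such requirement, so the share of opioid users is unknown.
- Section 7.3 gives its visit-by-visit example for BPI, not for OMED. Counting OMED comparisons per visit is a reasonable reading, not a stated one.
- Duration of response has no analysis in Section 7.3, so the 11-week limit affects a defined quantity rather than a planned test.
- This is a 30-patient single-arm pilot in which response is reported descriptively.

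These points limit the size of the problem. They do not complete the four-way classification for opioid users at the two late visits.

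**Conclusion.** The concern holds. The schedule and the text contradict each other on opioid dose at 6 and 12 months, and the documents give no rule of precedence. If the table is followed, the response percentages for objective 2.1.1 and the OMED comparisons can be completed at 4 of 6 follow-ups. At most 33% of planned patient-evaluations then lack OMED, or about 16% under the assumed losses. BPI comparisons remain possible at all six follow-ups, and response through week 12 is intact.

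This should be fixed. It limits what a primary objective can report on durability, but it does not threaten the sample size or the early results. The gap in the duration of complete response is real but minor, because the duration of overall response already ends at stable pain or progression.

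**What to change.** Make the table and the text agree, in one of two ways.

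1. Tick the opioid logbook row in the 6-month and 12-month columns of Section 5.1. A record of opioid intake over the preceding 72 hours is enough. The cost is two ticks and a short record at visits where the BPI is already scheduled. This should be settled before patients reach 6 months, because a 72-hour dose not recorded at the time cannot be reliably recovered later.
2. If late opioid data are not wanted, restrict response category, OMED comparisons and duration of response to week 12 in Section 7.3, and label the 6- and 12-month results as pain only. Amend the Study Overview and Sections 1.1, 6.1.1 and 7.1 to match. The cost is a few text edits and the loss of opioid-adjusted durability.

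The first option keeps what objective 2.1.1 promises at every evaluation. Separately, change one sentence in Section 6.1.2 so that duration of complete response ends at the first evaluation that is no longer a complete response, whether partial response, stable pain or progression.
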